3.3 Subject included

No formal sample size calculation was done as this is an open-label extension trial.

Subjects with aPAP who have completed the IMPALA (MOL-PAP-002) trial will be eligible for this trial. Up to 90 subjects may be included. All subjects in need of treatment will receive inhaled molgramostim.

4 Analysis Sets

All subjects excluding screening failures will be included in the full analysis set.

All subjects with exposure within the trial will be included in the safety analysis set.

The full analysis set will be used for demographics and efficacy summaries and the safety analysis set will be used for safety summaries.

Only recorded data will be analyzed/presented and any subjects who have missing data will only have observed data reported, with no imputation for missing data.

4.1 Protocol Deviations

Before data base lock (DBL) all protocol deviations will be evaluated and classified as minor or major. The decisions will be documented. Major protocol deviations will be listed.

5 Planned Statistical Methods

5.1 Statistical Considerations

Baseline is the value measured on visit 1 before first administration of investigational product in SAV006-003. For variables/assessments not scheduled to be performed at baseline or that are missing at baseline, the baseline value is the value from the IMPALA (MOL-PAP-002) trial measured closest to visit 1.

Numerical data will be presented using number of subjects, mean, standard deviation, median, range (minimum and maximum), as well as number of missing data (if relevant).

All summary tables for categorical variables will display counts, percentages and number of missing data (if relevant) by treatment group.

All tables will include three treatment arms based on the randomized treatment from the IMPALA trial in combination with the current treatment in the presentation of data. The treatment labels will be:

- MOL OD / MOL INT
- MOL INT / MOL INT
- PBO / MOL INT

Furthermore, all tables will include a total column.

End of trial date is set to the date of completion/discontinuation as entered in the eCRF on the end of trial page.

All listings will be made based on all subjects. They will be sorted by treatment and then subject number. A column showing which analysis sets (FAS/Safety) the subject belongs to, will be included.

Due to early closure of the trial patients will perform the measurements as described in visit 7 even though their last visit might not be visit 7.

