10.8.5.2. Pregnancy Screen

A serum pregnancy test will be performed for female subjects of child-bearing potential at each visit. For subjects who have a gap between completion of IMPALA and Baseline (Visit 1), a urine pregnancy test will also be performed before dosing at Baseline (Visit 1) in order to immediately confirm that the subject is not pregnant. If treatment is not dispensed at Baseline (Visit 1), the urine pregnancy test will be performed at start of treatment. Female subjects of child-bearing potential will be instructed to conduct a monthly urine pregnancy test at home.

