3.2 Trial Design

The trial is an open-label, non-controlled, multi centre clinical trial of inhaled molgramostim in autoimmune pulmonary alveolar proteinosis (aPAP) patients.

Subjects with aPAP who have completed the IMPALA (MOL-PAP-002) trial will be eligible for this trial.

At the baseline visit, eligible subjects may continue or re-start treatment with inhaled molgramostim (300 µg) administered intermittently in cycles of seven days molgramostim, administered once daily, and seven days off treatment.

Trial visits will be conducted at 6-monthly intervals until the end of trial. Participating subjects will be encouraged to contact the clinic between visits if they experience adverse events (AEs) or worsening of aPAP, or if they have any other concerns.

During the trial, Whole Lung Lavage (WLL) will be applied as rescue therapy. The criterion for performing WLL is clinical worsening of aPAP based on symptoms, reduced exercise capacity and/or findings of hypoxemia or desaturation according to the investigator's judgement. The reason(s) for conducting WLL will be documented. Subjects undergoing WLL will continue treatment with molgramostim, unless discontinuation is medically required, according to investigator's discretion.

Subjects may discontinue molgramostim due to remission of aPAP, lack of response that requires a different treatment modality, or AEs. Subjects becoming pregnant will be required to discontinue treatment with molgramostim. Subjects who discontinue molgramostim will be encouraged to continue in the trial and attend visits according to the same schedule until end of the trial. Molgramostim treatment may be re-started if medically required. Subjects not requiring treatment at the Baseline visit may start molgramostim treatment during the trial if medically required.

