ECG	(X)	X	X	X	X	X	X		(X) ^d
Blood gas analysis ^e	(X)†	X	X	X	X	X	X		(X) ^d
Lung function tests ^f	(X)†	X	X	X	X	X	X		(X) ^d
6MWT ^g	(X)†	X	X	X	X	X	X		(X) ^d
Quality of Life (SGRQ)	(X)†	X	X	X	X	X	X		
DSS	(X)†	X	X	X	X	X	X		(X) ^d
Overall Clinical Assessment	X	X	X	X	X	X	X		X
CT Scan	(X) ^d	(X) ^d	(X) ^d	(X) ^d	(X) ^d	(X) ^d	(X) ^d		(X) ^d

Table 1: Visit	Visit 1	Visit 2	Visit 3	Visit 4	Visit 5	Visit 6	Visit 7	FU TC 2 wks after trial completion	Unscheduled
	Baseline ^a	Month 6	Month 12	Month 18	Month 24	Month 30	Month 36		
Time	0	Week 26	Week 52	Week 78	Week 104	Week 130	Week 156		
Visit Window	N/A	± 4wks	± 4 wks	± 4 wks	± 4 wks	± 4 wks	± 4 wks	+ 1 wk	
Laboratory Safety Analyses ^h	(X)	X	X	X	X	X	X		(X) ^d
AEs	X	X	X	X	X	X	X	X	X
PK samples (Italy only) ⁱ	X	X	X	X	X	X			
Medical history	X								
Dispense trial drug ^j	X	X	X	X	X	X			(X) ^d
Subject Diary Card ^k	X	X	X	X	X	X	X		
Compliance		X	X	X	X	X	X		(X) ^d
Study continuation or termination ^l		X	X	X	X	X	X		(X) ^d

FU = follow-up, TC = telephone call, WLL = whole lung lavage

^a Baseline (Visit 1) may coincide with the final visit of the IMPALA (MOL PAP 002) trial; if so, assessments performed at Visit 11 (for subjects enrolled under protocol MOL PAP 002 version 4.0 or later), or Visit 13 (subjects enrolled under a protocol version prior to version 4.0) may serve as the baseline assessments for this protocol. If more than 3 months have elapsed since completion of the IMPALA study to Baseline (Visit 1) the assessments must be repeated.

^b Requirement for WLL and if required, indication for procedure will be recorded. If WLL is performed date of WLL and type of WLL (unilateral, bilateral) will be recorded.

^c Serum pregnancy test at Baseline (Visit 1) and at all subsequent visits during treatment with inhaled molgramostim (pregnancy tests for subjects not receiving trial drug are not mandatory). A urine pregnancy test will also be performed at dosing at Baseline (Visit 1) to immediately confirm that the subject is not pregnant and meets the inclusion criterion for treatment. If treatment is not dispensed at Baseline (Visit 1) the urine pregnancy test will instead be performed at the first visit treatment is dispensed. Subjects will be requested to do monthly urine testing at home during treatment.

^d Only applicable if assessment is done according to clinical practice or medical need, e.g. in case of a clinical deterioration. If done, results will be recorded

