5.3 Subject Disposition

An overall summary table of subject disposition will be prepared with number of patients in the following categories (and sub-categories):

- Number of subjects included

- Withdrawals (potential reasons are remission of aPAP, lack of efficacy/worsening of disease, unacceptable AE, investigator decision, pregnancy, withdrawal by subject, lost to follow-up or other)
- Early terminators (patients who don't complete the trial according to protocol due to early termination of the trial).
- Completers

All information will be listed including the time (days) between completion of IMPALA and visit 1 in this trial.

A listing of screening failures will be presented including violations of inclusion and/or exclusion criteria.

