7.2.4 Whole Lung Lavage

The number of subjects experiencing whole lung lavage (WLL), and the number of WLLs events will be summarized by visit and overall. The summary will also include event rates (95% CI) adjusted for time in trial since visit 1. A separate summary will present the number of subjects and the number of events between IMPALA and IMPALA-X. A WLL event is defined as a WLL procedure performed on a unilateral lung. These events are entered at visit 1 as part of the overall clinical assessment.

Time in trial is defined as the number of days from visit 1 to end of trial date.

Event rates shown as the number of events per subject year and the 95% confidence intervals (CI) of the event rates are estimated using a negative binomial model.

The 95% CI will be estimated using the below piece of code in SAS. Here the dataset *wll_rate* has the number of whole lung lavage by subject in parameter *aval*, and the logarithm of the time of exposure in parameter called *log_dur*. The parameter one has the value 1 (one) for all subjects. The dataset final include the estimated rate (*esti*), and the lower limit of the confidence interval (*lowci*) and the upper limit of the confidence interval (*uppci*).

```
ods output ParameterEstimates=ParameterEstimates;

proc genmod data= wll_rate;

class one;

model aval= one /cl noint dist=negbin offset=log_dur link=log ;

lsmeans one / exp cl;

run;

data exp;

set ParameterEstimates;

where parameter="one";

esti = exp(estimate); * estimate;

lowci = exp(LowerWaldCL); * lower limit of confidence interval;

uppci = exp(UpperWaldCL); * upper limit confidence interval;

run;
```

Furthermore, the whole lung lavage will be summarized by location (left, right or both) and the volume of saline used will be summarized.

A listing of subjects requiring WLL including reasons for WLL, date of criteria met, and date of procedure will be provided.

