- Listing 16.2.6.8 Individual overall clinical assessments (all subjects)
- Listing 16.2.6.9 Individual GM-CSF measurements above lower level of quantification (all subjects)
- Listing 16.2.7.1 Adverse events (all subjects)
- Listing 16.2.7.2 Serious adverse events (all subjects)

Listing 16.2.7.3 Adverse drug reactions (all subjects)

Listing 16.2.7.4 Adverse events leading to treatment discontinuation (all subjects)

Listing 16.2.8.1 Individual haematology (all subjects)

Listing 16.2.8.2 Individual clinical chemistry (all subjects)

Listing 16.2.9.1 Individual vital signs (all subjects)

Listing 16.2.9.2 Individual electrocardiogram (all subjects)

Listing 16.2.10.1 Individual CT scans (all subjects)

13 List of Tables

Section 14.1

Table 14.1.1 Subject disposition (full analysis set)

Table 14.1.2 Number of subjects by visit (full analysis set)

Table 14.1.3 Baseline demographics (full analysis set)

Table 14.1.4 Medical history (full analysis set)

Table 14.1.5 Summary of exposure (months) (safety analysis set)

Table 14.1.6 Summary of cumulative exposure (safety analysis set)

Table 14.1.7 Summary of relative exposure (safety analysis set)

Table 14.1.8 Summary of last visit attended (full analysis set)

Table 14.1.9 Concomitant medication (safety analysis set)

Table 14.1.10. Summary of missed key secondary endpoints assessments due to COVID-19 pandemic (safety analysis set)

Table 14.1.11 Summary of alternative endpoint ascertainment due to COVID-19 pandemic (safety analysis set)

Section 14.2

(14.2.1: Blood gas analysis endpoints)

Table 14.2.1.1 Summary of (A-a)DO₂ (mmHg) (full analysis set)

Table 14.2.1.2 Summary of change from baseline in (A-a)DO₂ (mmHg) (full analysis set)

(14.2.2: 6 minutes walking test endpoints)

Table 14.2.2.1 Summary of 6 minutes walking distance (m) (full analysis set)

Table 14.2.2.2 Summary of change from baseline in 6 minutes walking distance (m) (full analysis set)

Table 14.2.2.3 Summary of pre-walk dyspnoea score (Borg CR10) (full analysis set)

Table 14.2.2.4 Summary of change from baseline in 6 minutes walking distance (m) (full analysis set)

Table 14.2.2.5 Summary of post-walk dyspnoea score (Borg CR10) (full analysis set)

Table 14.2.2.6 Summary of change from baseline in dyspnoea score (Borg CR10) (full analysis set)

Table 14.2.2.7 Summary of SpO₂ at start of walk (%) (full analysis set)

Table 14.2.2.8 Summary of change from baseline in SpO₂ at start of walk (%) (full analysis set)

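### The SAP's fallback baseline has no limit on age and no lavage condition, so change that happened before Visit 1 can be reported as change during the extension

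*SAP*

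**What the plan says.** SAP 5.1 defines baseline as the Visit 1 measurement taken before the first dose in this trial. It then adds a fallback for anything that was not planned at that visit or has no recorded result there. In those cases, "the baseline value is the value from the IMPALA (MOL-PAP-002) trial measured closest to visit 1". The rule gives no maximum age for that value and does not ask whether anything happened to the subject between the measurement and Visit 1.

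Note a of the flow chart (protocol Table 1, repeated in SAP Table 1) allows final-visit IMPALA assessments to serve as baseline when the two visits coincide. It continues: "If more than 3 months have elapsed since completion of the IMPALA study to Baseline (Visit 1) the assessments must be repeated".

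Both documents expect some subjects to arrive after an interval:

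- SAP 3.2 says that "eligible subjects may continue or re-start treatment with inhaled molgramostim".
- Protocol 10.8.5.2 has a separate pregnancy-test rule, which begins "For subjects who have a gap between completion of IMPALA and Baseline (Visit 1").
- SAP 7.2.4 plans for lavages in the interval: "A separate summary will present the number of subjects and the number of events between IMPALA and IMPALA-X".
- SAP 5.3 lists the length of the interval: "All information will be listed including the time (days) between completion of IMPALA and visit 1 in this trial".

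SAP section 9, which records deviations from the protocol, does not mention the baseline rule.

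**The concern.** A change from baseline in an extension trial should describe what happened after entry to the extension. If the starting value was measured in IMPALA, and the subject then spent time off drug or had a lavage before Visit 1, the change contains two parts: what happened before Visit 1 and what happened after it. The tables cannot separate them.

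SAP section 13 plans change-from-baseline tables for (A-a)DO₂, the walk test variables, the St George's questionnaire scores, DLCO, FEV₁, FVC and the disease severity score, and also for vital signs, ECG and laboratory data. Exposure (SAP 6.1) and time in trial (SAP 7.2.4) both start at Visit 1. For a subject with a fallback baseline, change would therefore run over a longer period than the exposure shown for that subject. SAP 7.2.6 describes the severity-score comparison as starting from Visit 1, which would not be true for such a subject.

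**Working it through.** The plan states no figure to reproduce. The trial is descriptive and has no sample size calculation. The check is a comparison of the two rules, followed by an illustration of scale.

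**Step 1. Where the two rules meet**, for a subject whose Visit 1 value may be missing:

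| Interval from IMPALA completion to Visit 1 | Note a | SAP 5.1 | Result |
|---|---|---|---|
| Visits coincide | IMPALA final-visit value may serve | Visit 1 value, or closest IMPALA value | Consistent |
| Gap of 3 months or less | No repeat demanded; reuse not expressly addressed | If missing, closest IMPALA value | No direct conflict, but the value may precede a lavage |
| More than 3 months, repeat done | Repeat required | Visit 1 value used | Consistent |
| More than 3 months, repeat missed | Repeat required | Closest IMPALA value, whatever its age | Direct conflict |

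So there are two exposed cases: the missed repeat, and the lavage within a short gap.

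**Step 2. What a fallback baseline does.** Let V be the true Visit 1 value, B the IMPALA value and Y a later value.

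Reported change = Y − B = (Y − V) + (V − B)

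The second bracket is change before Visit 1. For (A-a)DO₂, where lower is better, deterioration off drug makes V − B positive and the extension looks worse. Improvement after a lavage makes it negative and the extension looks better.

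**Step 3. Scale, under assumptions.** Inputs:

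- n = 60 enrolled (SAP 3.2).
- k = number of subjects with a misplaced baseline. The documents do not give it; 3, 6 and 12 are assumed.
- d = size of V − B in mmHg. The documents do not give it. As a scale only, protocol 4.1 cites a trial with a mean on-treatment reduction in (A-a)DO₂ of 12.3 (8.4–16.2) mmHg.

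Shift in mean change = (k / n) × d, if all errors have the same sign:

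| k of 60 | d = 8.4 | d = 12.3 | d = 16.2 |
|---|---|---|---|
| 3 (5%) | 0.42 | 0.62 | 0.81 |
| 6 (10%) | 0.84 | 1.23 | 1.62 |
| 12 (20%) | 1.68 | 2.46 | 3.24 |

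Only the fraction matters. If the three treatment columns held 20 subjects each (an assumption, 60 / 3), 2 of 20 would give the 10% row.

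Mixed signs shrink the shift. With 6 affected at d = 12.3, 4 worsened and 2 improved, it is (4 − 2) / 60 × 12.3 = 0.41 mmHg. With 3 and 3 it is zero.

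**The case against.** The strongest defence is that the rules agree whenever the protocol is followed. Beyond 3 months a repeat is mandatory, so a Visit 1 value exists and SAP 5.1 uses it. The direct conflict needs a protocol deviation. This is correct, and it confines the first half of the point to missed repeats.

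Three stronger readings are tempting, and the documents do not support them.

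- A reader might infer that note a declares IMPALA values older than 3 months unusable for analysis. It does not. It governs the conduct of visits, counts from IMPALA completion rather than from the measurement date, and does not say how to analyse a missed repeat.
- A reader might infer that the lavage problem is also a contradiction. It is not. Neither document makes absence of lavage a condition for baseline. That condition is a recommendation, prompted by the SAP's own expectation of lavages between the trials.
- A reader might infer a known bias concentrated in subjects with long gaps. Nothing shows that their Visit 1 values are missing, and the two mechanisms act in opposite directions. The 12.3 mmHg figure is an improvement on treatment, not drift during a gap. Protocol 4.1 also reports that the published results indicate benefit lasting more than a year after stopping, which weighs against assuming large drift.

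It is also fair to say that much is visible already. Interval length is listed, between-trial lavages have their own table, protocol deviations are classified before database lock, and absolute values by visit stand beside the change tables. What remains is that no planned output shows which baselines came from the fallback, so a reader of a change table cannot tell whether it is affected.

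**Conclusion.** The point holds in a limited form. SAP 5.1 places no age limit and no lavage condition on the fallback. It directly conflicts with note a only where a required repeat was missed. Separately, for gaps of 3 months or less, it allows a baseline from before a between-trial lavage. In both cases change before Visit 1 is reported as change during the extension.

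The size is unknown. Under the assumptions above, the shift in mean (A-a)DO₂ change runs from 0.42 to 3.24 mmHg when all errors share a sign, and can fall to zero when they do not or when no subject is affected. The affected outputs are descriptive change tables, secondary and safety. The primary adverse event endpoints and all post-baseline absolute values are unaffected. This is a cheap improvement rather than a threat to the trial's main conclusions.

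**What to change.** Amend SAP 5.1 so that the IMPALA fallback is used only when both conditions hold:

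1. Visit 1 falls within 3 months of IMPALA completion, which is note a's own clock.
2. No WLL was done between the IMPALA measurement and Visit 1.

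Otherwise set baseline to missing for the change-from-baseline tables. This also fits the observed-data-only rule in SAP sections 4 and 7.4. Flag fallback baselines in the listings and report their number. Showing the measurement date with the flag would help, because note a's clock does not cap the age of a value taken before the final IMPALA visit.

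If losing subjects is the greater worry, keep the present fallback, flag it, and repeat the change tables without the flagged subjects.

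The cost is a sentence or two in the SAP and one flag. Interval length and between-trial lavages are already planned for output. The downside of the restriction is that a few subjects lose change-from-baseline values; their absolute values by visit remain in the tables.

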5.2 Data Issues due to Covid-19 Pandemic

To get an overview of the impact the COVID-19 pandemic has on the trial the below output will be presented

- Listing with COVID-19 positive subjects including country and time since trial start to COVID-19 start date
- Listing of all adverse events occurring in COVID-19 positive patients including time of the adverse event relative to the COVID-19 start date
- Table with number of missed key secondary endpoints assessments due to pandemic by treatment and visit. The key secondary endpoints are (A-a)DO₂, 6MWD, SGRQ total, DLCO (% predicted), PaO₂ and DSS
- Table with number of alternative endpoint ascertainment (telephone visits, allowed out of window visits and such) if any due to COVID-19 by treatment and visit
- Listing with all protocol deviations due to COVID-19

5.3 Subject Disposition

An overall summary table of subject disposition will be prepared with number of patients in the following categories (and sub-categories):

- Number of subjects included

- Withdrawals (potential reasons are remission of aPAP, lack of efficacy/worsening of disease, unacceptable AE, investigator decision, pregnancy, withdrawal by subject, lost to follow-up or other)
- Early terminators (patients who don't complete the trial according to protocol due to early termination of the trial).
- Completers

All information will be listed including the time (days) between completion of IMPALA and visit 1 in this trial.

A listing of screening failures will be presented including violations of inclusion and/or exclusion criteria.

5.4 Baseline Demographics

Baseline demographics consists of age, sex, race, body weight, height and BMI. Baseline demographic information will be listed and summarized using descriptive statistics. The table will also include number and percentage of patients in age groups < 65 years and ≥ 65 years.

5.5 Medical History

Medical history will be recorded at visit 1 and coded using medDRA version 21.0.

Medical history will be summarized and listed.

6 Exposure and Other Dosing Information

6.1 Exposure

Treatment with molgramostim at least once during the trial (yes/no) will be summarized by treatment.

Exposure will be summarized by treatment showing summary statistics (mean, standard deviation, median, p25, p75, minimum and maximum).

Furthermore, an output will be generated showing number of subjects with ≥ 6 months exposure, ≥ 12 months exposure, ≥ 18 months exposure etc.

Exposure will be defined as number of days from visit 1 to last kit date + 21 days or end of trial date whatever comes first.

For the safety update (see section 8.2) exposure will be calculated as number of days from visit 1 to Last kit date + 21 days or Date of last visit before cut-off for safety update whatever comes first.

Relative exposure will be defined as

$$\text{Relative exposure} = \text{Exposure} / \text{number of days in trial}$$

where exposure is defined above. Relative exposure will be summarized by treatment and listed.

Due to premature trial closure a table with last visit attended will be presented showing number of patients and percentages. For patients where the last visit was entered as visit 7, the original visit they came in for will be presented in this table based on full analysis set. A listing of visits attended will be presented.

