6. INVESTIGATIONAL PLAN

6.1. Overall Study Design

Subjects with aPAP who have completed the IMPALA (MOL-PAP-002) trial will be eligible for this trial.

At the Baseline visit, eligible subjects may continue or re-start treatment with inhaled molgramostim (300 µg) administered intermittently in cycles of seven days molgramostim, administered once daily, and seven days off treatment.

Trial visits will be conducted at 6-monthly intervals until the end of trial. Participating subjects will be encouraged to contact the clinic between visits if they experience AEs or worsening of aPAP, or if they have any other concerns.

During the trial, WLL will be applied as rescue therapy. The criterion for performing WLL is clinical worsening of aPAP based on symptoms, reduced exercise capacity and/or findings of hypoxemia or desaturation according to the investigator's judgement. The reason(s) for conducting WLL will be documented. Subjects undergoing WLL will continue treatment with molgramostim, unless discontinuation is medically required, according to investigator's discretion.

Subjects may discontinue molgramostim due to remission of aPAP, lack of response that requires a different treatment modality, or AEs. Subjects becoming pregnant will be required to discontinue treatment with molgramostim. Subjects who discontinue molgramostim will continue in the trial and attend visits according to the same schedule until end of the trial. Molgramostim treatment may be re-started if medically required. Subjects not requiring treatment at the Baseline visit may start molgramostim treatment during the trial if medically required.

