7.3. Subject Withdrawal Criteria

7.3.1. Discontinuation of Trial Treatment

Subjects may be discontinued from treatment and assessments at any time, if deemed necessary by the investigator. Potential reasons for discontinuation of treatment are:

- Remission of aPAP
- Lack of efficacy/worsening of disease (e.g. loss of response that requires a different treatment modality).
- Unacceptable AE (including serious hypersensitivity reaction).
- Pregnancy.

Those who discontinue treatment will not automatically be withdrawn from the trial but will be encouraged to continue to follow the same visit schedule. If medically indicated and no safety-related exclusion criteria have emerged, treatment may be restarted at a later visit.

The reason and date the subject is discontinued will be documented in the electronic case report form (eCRF).

Subjects who fulfil the criteria for rescue treatment will be scheduled for a WLL as described in Section 10.2. Subjects receiving a WLL should continue treatment and attend the remaining visits, unless discontinuation is medically required, according to investigator's discretion.

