8.1.1 Analysis and Presentation of Safety Parameters

8.1.2 Adverse Events

All adverse events (AEs) occurring after informed consent will be reported in the eCRF. AEs will be coded using the Medical Dictionary for Regulatory Activities (MedDRA) version 21.0.

Adverse events are considered treatment emergent if the onset of the events is on or after the first exposure date of IMP in this trial and until (estimated) last drug date + 7 days. Last drug date is defined as last kit date + 21 days or end of trial date whatever comes first. Only treatment emergent events will be included in the safety summaries.

Possible or probable related AE's are defined as ADRs.

Adverse events will be presented as described in section 7.1.

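### SAP 6.1 counts exposure as one unbroken interval from visit 1 rather than from the first dose in this trial, and ends it from a last kit date that is not defined

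*SAP*

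**What the plan says.** SAP 6.1 sets the rule for the final report: "Exposure will be defined as number of days from visit 1 to last kit date + 21 days or end of trial date", whichever is earlier. For the safety update, "exposure will be calculated as number of days from visit 1 to Last kit date + 21 days", with the last visit before cut-off as the alternative end. Relative exposure divides that figure by days in trial. Neither definition provides for a later first dose or a period off drug.

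Both situations are allowed. SAP 3.2 says "Subjects not requiring treatment at the Baseline visit may start molgramostim treatment during the trial if medically required", and Protocol 6.1 says "Molgramostim treatment may be re-started if medically required". SAP 9 adds that, contrary to what was expected when the protocol was written, some patients are not treated in this trial. A safety analysis set was added for that reason.

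SAP 8.1.2 uses a different start. An adverse event is treatment-emergent if its onset is "on or after the first exposure date of IMP in this trial" and no later than 7 days after the last drug date. It then states: "Last drug date is defined as last kit date + 21 days or end of trial date whatever comes first". It also states: "Only treatment emergent events will be included in the safety summaries".

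The last kit date appears only in SAP 6.1 and 8.1.2, and the available text does not define it. Protocol 9.2 has 26 weeks of medication supplied at dispensing visits, Protocol 9.3 has used and unused drug returned at the next clinic visit, and Protocol 10.5 has subjects put the tear-off box label in the diary.

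**The concern.** Long-term safety is the primary objective, and Tables 14.1.5 to 14.1.7 tell the reader how much long-term use stands behind the safety data. Under SAP 6.1, two subjects with the same visit 1, last kit date and end of trial receive the same exposure, even if one was treated for half as long as the other. The SAP already needs the correct start date for its adverse event window, so it works with two start dates for one treatment period.

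The undefined end date reaches further. It closes exposure and also decides which late events enter the adverse event tables and which appear only in listings. SAP 7.1 plans a rate of events without stating its denominator. If the denominator is exposure, numerator and denominator would start on different days.

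**Working it through.** The documents give no computed exposure figure, so there is nothing to reproduce. The check applies the SAP's date arithmetic to the planned visit grid.

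**Inputs**
- Visits 26 weeks (182 days) apart: days 0, 182, 364, 546, 728, 910 and 1092 (Protocol Table 1).
- 26 weeks (182 days) supplied at a dispensing visit (Protocol 9.2).
- 21 days added to the last kit date (SAP 6.1 and 8.1.2), and a further 7 days for the treatment-emergent window (SAP 8.1.2).
- 55 subjects on treatment at termination (SAP 3.2).
- Assumed for illustration: end of trial at week 104 (day 728), visits on their nominal days, and the individual start and stop days used below.

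**Start rule and gaps**

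Exposure under SAP 6.1 = min(last kit date + 21, end of trial) − visit 1.

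| Subject | Days on treatment | SAP 6.1, late kit date | SAP 6.1, kit date = last dispensing (day 546) |
|---|---|---|---|
| Dosed from visit 1, no break | 728 | 728 | 546 + 21 = 567 |
| First dose at week 52 | 728 − 364 = 364 | 728 | 567 |
| Off drug weeks 26 to 78 | 182 + 182 = 364 | 728 | 567 |

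True relative exposure for the week-52 starter is 364/728 = 50%. SAP 6.1 reports 728/728 = 100% or 567/728 = 78%. The row for at least 18 months needs 18 × 30.44 = 548 days. Both reported figures pass it and the true one does not.

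Moving the start to first dose corrects the second row but not the third. Time between courses is counted because the interval is unbroken, so gaps need a rule of their own.

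**Pooled size, assuming 55 subjects followed for 104 weeks and one week-52 starter**
- True total: 54 × 728 + 364 = 39,676 days.
- Late kit date: 55 × 728 = 40,040 days, or +0.9%.
- Dispensing date: 55 × 567 = 31,185 days, or −21.4%, almost all of it from the end rule.

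On the dispensing-date reading the end rule removes 182 − 21 = 161 days from a subject who uses the last supply to the end. Delays or gaps shorter than 161 days therefore give a net understatement.

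**Three readings of last kit date**
- *Dispensing date.* The treatment-emergent window closes 21 + 7 = 28 days after the last dispensing, so up to 182 − 28 = 154 of the last 182 supplied days fall outside it. The figure is 154 − 28 = 126 if the final visit is four weeks early.
- *Return date.* Suppose a subject receives drug on day 546, stops mid-interval on day 546 + 91 = 637, returns it on day 728 and stays in the trial. Exposure runs to 728 + 21 = 749, which is 112 days past the last dose. The window runs to day 756, 119 days past it.
- *Opening date.* An assumed box of 14 doses lasts 7 on + 7 off + 7 on = 21 days. A continuous user then loses neither exposure nor adverse event time.

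**The case against.** The strongest reply is that no consequence is shown. The documents permit late starts and re-starts but report none. Protocol 9.5 gives the first dose at visit 1 to subjects treated from Baseline, so for them the two start dates coincide. The 100% against 50% contrast describes one hypothetical subject, and the pooled illustration on a late kit date is under 1%. All of that stands and limits the size of the point, but it does not make the definition right for the subjects to whom it would apply.

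It can also be said that adding 21 days to a 26-week supply makes little sense, so the dispensing-date reading is the least natural and its large figures are worst cases. That is fair. A 21-day box is coherent, but it is an assumption, and Protocol 9.2 leaves the dispensing reading open.

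Other outputs help in part. Table 14.2.8.2 shows treatment requirement since the last visit, and Listing 16.2.7.1 carries every adverse event. Neither corrects the exposure tables. SAP 9 also concedes insufficient data on time off treatment, so some gaps may not be removable.

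A reader might infer three stronger things that the documents do not support:
- *Never-treated subjects inflate the exposure tables.* They do not, because Tables 14.1.5 to 14.1.7 use the safety analysis set.
- *The five subjects off treatment at termination are late starters or interrupters.* SAP 3.2 gives only their status at that time.
- *Time after the final stop is always cut off by the kit-date rule.* It is not if the kit date is a return date.

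**Conclusion.** The rule is wrong as written for any late starter and for any subject with an off-treatment gap. Measured to the same end date, their exposure is overstated by the length of the delay or gap. That is 364 days in the worked cases, with relative exposure for the week-52 starter at 100% instead of 50% when the kit date is late. Subjects dosed at visit 1 and treated without interruption are not affected by the start rule.

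The trial-wide effect is unknown because the number of affected subjects is not given. It may be small: +0.9% under the assumption of one week-52 starter among 55 subjects, all followed for 104 weeks. The net direction for the trial cannot be stated either, since a dispensing-date reading shortens exposure while the start rule lengthens it.

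The undefined last kit date is a secondary point. The text does not support a claim that late adverse events will be left out of the summaries, or that the window will over-extend; each follows from one reading only. It does support the need for a definition before either output can be interpreted. This should be fixed. Confidence is high on the wording and low on the practical size.

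**What to change.** - **Start.** In SAP 6.1, count from the first dose of investigational product in this trial, the date SAP 8.1.2 already requires.
- **Gaps.** Subtract time between courses where stop and re-start dates are recorded, and keep the scheduled 7-day off periods as exposed time. Where dates are missing, label the result as time from first to last dose and disclose the remaining overcount.
- **End.** Define the last kit date and give the basis for the 21 days. If it is a dispensing or return date, set the last drug date to the final recorded treatment stop, meaning the last stop and not the first for subjects who re-started. Protocol 7.3.1 requires the discontinuation date in the eCRF. Where none is recorded, use the earlier of end of trial and last dispensing date plus the period supplied. Keep the existing 7 days after the last drug date for the treatment-emergent window.
- **Rate.** State the denominator of the adverse event rate in SAP 7.1.

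Cost: Tables 14.1.5 to 14.1.7 and Listings 16.2.5.1 and 16.2.5.2 are re-derived. The adverse event tables (14.3.1.1 to 14.3.1.23) are re-run if the end rule changes, and the affected ones if exposure proves to be the rate denominator. Stated exposure becomes shorter for late starters. A safety update already issued (planned cut-off 1 February 2019) need not be re-run, but the clinical trial report should note the difference in definition.
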